## 9.5. Reporting Adverse Events

The Investigator is responsible for reporting all AEs that are observed or reported after the first dose of patisiran regardless of their relationship to patisiran administration through the end of the study.

Any medical condition that is present when the patient enters this extension study and does not deteriorate should not be reported as an AE. However, if it does deteriorate at any time during the study, it should be reported as an AE.

All AEs must be fully recorded in the site's source records and in the patients' CRF, whether or not they are considered to be drug-related. Each AE should be described in detail: onset time and date, description of event, severity, relationship to investigational product, action taken, and outcome (including time and date of resolution, if applicable).

Adverse events should be followed through the end of study visit or until recovery to the normal state has been achieved, whichever occurs first. In the event of a patient not returning to the clinical unit, the outcome of this event will be recorded as lost to follow-up.

For patients who withdraw from the study early, ongoing AEs will be followed until resolution or 28 days from last dose, whichever occurs first. SAEs will be followed by the Investigator until satisfactory resolution or the Investigator deems the SAE to be chronic or stable.

### 9.5.1. Serious Adverse Event Reporting

An assessment of the seriousness of each AE will be made by the Investigator. Any AE and laboratory abnormality that meets the above seriousness criteria (Section 9.2.1.2) must be reported immediately to the CRO, always within 24 hours from the time that site personnel first learn of the event. All SAEs must be reported regardless of the relationship to patisiran.

The initial report should include at least the following information:

- Patient's study number
- Description and date of onset of the event
- Criterion for serious
- Preliminary assignment of causality

Serious AE reporting will be via electronic data capture (EDC).

To report the SAE, complete the SAE form electronically in the EDC system for the study. If the event meets serious criteria and it is not possible to access the EDC system, send an email to Medpace Safety at PPD or call the Medpace SAE hotline listed below (country-specific phone number will be provided in the Study Manual), and fax the completed back-up paper SAE form to Medpace (country-specific fax number will be provided in the Study Manual) within 24 hours of awareness. When the form is completed, Medpace Safety personnel will be notified electronically and will retrieve the form. When the EDC system becomes available, the SAE information must be entered into the EDC system within 24 hours of the system becoming available. Medpace Safety personnel will be available for SAE reporting on a 24 hour basis. Incoming reports will be reviewed during normal business hours.

Medpace SAE hotline – USA:

Telephone: PPD ext. PPD or PPD ext. PPD

Facsimile: PPD or PPD

Medpace SAE hotline – Europe:

Telephone: PPD

Facsimile: PPD

Within 24 hours of receipt of follow-up information, the investigator must update the SAE form electronically in the EDC system for the study and submit any supporting documentation (eg, patient discharge summary or autopsy reports) to Medpace Safety personnel via fax or e-mail. If it is not possible to access the EDC system, refer to the procedures outlined above for initial reporting of SAEs.

Appropriate remedial measures should be taken by the Investigator using his/her best medical judgment to treat the SAE. These measures and the patient's response to these measures should be recorded. All SAEs, regardless of causality, will be followed by the Investigator until satisfactory resolution or the Investigator deems the SAE to be chronic or stable. Clinical, laboratory, and diagnostic measures should be employed by the Investigator as needed to adequately determine the etiology of the event.

The Investigator will be responsible for reporting all SAEs to the local IEC or IRB when required by national regulations.

The Sponsor or its representative will be responsible for the reporting of all relevant events to the concerned regulatory authorities according to all applicable regulations.

In Europe, in accordance with the Directive 2001/20/EC, the Competent Authorities and the Ethics Committees in the concerned Member States will be notified of fatal and life-threatening Suspected Unexpected Serious Adverse Reactions (SUSARs) as soon as possible but no later than 7 calendar days after the Sponsor or its representative has first knowledge of the minimum criteria for expedited reporting. Non-fatal and non-life-threatening SUSARs should be reported no later than 15 calendar days after the Sponsor or its representative has first knowledge of them.

The Investigator may be informed by the Sponsor or its representative of SAEs from other Investigators or clinical studies which may have relevance to this clinical study. These SAEs should also be reported promptly to the IEC/IRB that approved the study. All SAE reports should be transmitted to the IEC/IRB with a cover letter or transmittal form, and a copy of that

transmittal should be maintained in the Investigator's files and forwarded to the Sponsor as part of the trial master file on study completion.

### **9.5.2. Pregnancy Reporting**

A female patient must have a negative pregnancy test within 14 days before the first dose of patisiran on this study. If a female patient is found to be pregnant during the course of the study or during the first month after receiving the last dose of patisiran, the Investigator should report the pregnancy to the CRO within 24 hours of being notified of the pregnancy. Details of the pregnancy will be recorded on the pregnancy reporting form. Treatment with patisiran will be discontinued in any patient who is found to be pregnant during the study. The patient should receive any necessary counseling regarding the risks of continuing the pregnancy and the possible effects on the fetus.

The pregnancy should be followed by the Investigator until completion. At the completion of the pregnancy, the Investigator will document the outcome of the pregnancy. If the outcome of the pregnancy meets the criteria for an SAE (ie, postpartum complication, spontaneous abortion, stillbirth, neonatal death, or congenital anomaly), then the Investigator should follow the procedures for reporting an SAE outlined above.

Pregnancy occurring in the partner of a patient participating in the study should also be reported to the Investigator, who will then report this to the CRO and follow to outcome as described above.

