### 1.2. Patisiran

Patisiran (the International Nonproprietary Name [INN] name for the drug product also referred to as ALN-TTR02) is a novel investigational agent being developed for the treatment of ATTR patients with symptomatic FAP. Patisiran comprises a small interfering ribonucleic acid (siRNA) which is specific for TTR, and is formulated in a hepatotropic lipid nanoparticle (LNP) for intravenous (IV) administration. It is designed to significantly suppress liver production of both WT and all mutant forms of TTR, thereby having the potential to reduce amyloid formation and provide clinical benefit to patients with FAP.

The nonclinical pharmacology, pharmacokinetics (PK), and toxicology of patisiran were evaluated in a series of in vitro and in vivo studies that have enabled chronic dosing in clinical studies. A summary of the nonclinical data can be found in the patisiran Investigators Brochure (IB).

In a Phase 1 study of patisiran in healthy volunteers (Study ALN-TTR02-001), patisiran was generally well tolerated. Significant pharmacology in terms of TTR protein lowering (>80% reduction from pretreatment baseline) was observed at doses  $\geq 0.15$  mg/kg. TTR levels showed evidence of recovery at Day 28 and return to baseline by Day 70. A Phase 1 study in healthy

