## 4. SELECTION AND WITHDRAWAL OF PATIENTS

### 4.1. Patient Inclusion Criteria

To be enrolled in the study, patients must meet the following criteria before administration of patisiran on Day 0:

1. Have completed a patisiran study (ie, completed the last efficacy visit in the parent study) and, in the opinion of the investigator, tolerated study drug
2. Be considered fit for the study by the Investigator
3. Have aspartate transaminase (AST) and alanine transaminase (ALT) levels  $\leq 2.5 \times$  the upper limit of normal (ULN), international normalized ratio (INR)  $\leq 2.0$  (patients on anticoagulant therapy with an INR of  $\leq 3.5$  will be allowed)
4. Have a total bilirubin within normal limits. A patient with total bilirubin  $\leq 2 \times$  ULN is eligible if the elevation is secondary to documented Gilbert's syndrome (elevation of unconjugated bilirubin with normal conjugated bilirubin) and the patient has ALT and AST levels within normal ranges.
5. Have a serum creatinine  $\leq 2 \times$  ULN
6. Women of child-bearing potential must have a negative pregnancy test, cannot be breastfeeding, and must be using 2 highly effective methods of contraception prior to dosing in this study and agree to use 2 highly effective methods of contraception throughout study participation and for 75 days after last dose of patisiran in this study. Highly effective methods of birth control are defined in Section 4.4.
7. Males with partners of child-bearing potential must agree to use 1 barrier method (eg, condom) and 1 additional method (eg, spermicide) of contraception throughout study participation and for 75 days after the last dose of patisiran in this study; males must also abstain from sperm donation after the first dose of patisiran through study participation and for 75 days after last dose of patisiran in this study
8. Be willing and able to comply with the protocol-required visit schedule and visit requirements and provide written informed consent

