### 4.3. Patient Withdrawal Criteria

Patients are free to withdraw from the study at any time and for any reason, without penalty to their continuing medical care. For those patients who withdraw, every effort will be made to determine their reason for dropping out, and to complete the Early Withdrawal visit.

The Investigator may withdraw a patient from the study if the patient:

- Is in violation of the protocol
- Experiences a serious or intolerable AE
- Becomes pregnant
- Requires a prohibited medication (see Section 5.2)
- Requests to be withdrawn from the study
- Is found to be considerably noncompliant with the protocol-required patisiran dosing visits

The Investigator will withdraw patients from the study upon the request of the Sponsor, including if the Sponsor terminates the study. Upon occurrence of a serious or intolerable AE, the Investigator will confer with the Sponsor before discontinuing the patient.

Missing an occasional dose of patisiran will not necessarily result in the patient being withdrawn from the study. However, if a patient misses 3 consecutive doses of patisiran, the Investigator at the clinical site and the Medical Monitor will determine whether the patient should be withdrawn from the study. If the patient is withdrawn from the study, the reason will be noted in the patient medical record and on the case report form (CRF).

In the event a patient is withdrawn from the study, the clinical research organization (CRO) Medical Monitor must be informed immediately.

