### 4.4. Pregnancy and Breastfeeding Restrictions / Contraception Requirements

TTR transports vitamin A in plasma; therefore, reductions in circulating vitamin A levels accompany reductions in TTR caused by patisiran. Vitamin A deficiency has known effects on both male and female reproductive performance and embryo/fetal development. It is not known whether decreased levels of vitamin A at efficacious patisiran doses in ATTR patients who are male or who are women of child bearing potential will affect reproduction. Histopathological evaluations of all of the reproductive organs have been conducted in the rat and non-human primate (NHP) toxicology studies including a chronic NHP study in sexually mature animals, where there were no adverse effects in males (including sperm analyses and spermatogenic staging) or females. In a dose range-finding rat embryo/fetal development study

conducted with patisiran, there were no effects on mating, fertility, ovarian or uterine parameters, or fetal development despite reductions (-88% from baseline) in serum vitamin A in the dams dosed with the rat-specific TTR surrogate siRNA.

Women of child-bearing potential are defined as any woman or adolescent who has begun menstruation. A post-menopausal woman is defined as a woman who has 12 months of spontaneous amenorrhea or 6 months of spontaneous amenorrhea with serum FSH levels >40 mIU/mL or 6 weeks postsurgical bilateral oophorectomy with or without hysterectomy.

In this study, women of child-bearing potential must have a negative pregnancy test, cannot be breastfeeding, and must be using 2 highly effective methods of contraception prior to dosing on Day 0, throughout study participation, and for 75 days after last dose of patisiran in this study. Highly effective methods of birth control result in a low failure rate (ie, less than 1% per year). Acceptable forms of effective contraception are defined as follows:

- Hormonal: established use of oral, implantable, injectable, or transdermal hormonal methods of conception
- Placement of an intrauterine device (IUD)
- Placement of an intrauterine system (IUS)
- Mechanical/barrier method of contraception: condom or occlusive cap (diaphragm or cervical/vault cap) in conjunction with spermicide (foam, gel, film, cream or suppository)

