Males (including men who have had vasectomies) with partners of child-bearing potential, must agree to use 1 barrier method (eg, condom) and 1 additional method (eg, spermicidal foam, gel, film, cream, or suppository) of contraception throughout study participation and for 75 days (ie, a whole spermatogenic cycle) after the last dose of patisiran in this study. Males must also abstain from sperm donation after the first dose of patisiran through study participation and for 75 days after last dose of patisiran in this study.

In Japan it is recommended that the Investigators select appropriate contraception methods, as available.

Pregnancy reporting guidelines are provided in Section [9.5.2](#).

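### For female patients, required pregnancy reporting stops about a month after the last dose, although the protocol requires contraception for 75 days

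*Protocol*

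**What the plan says.** The current global protocol (version 3.0) sets two post-dose periods that bear on pregnancy in female patients.

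- **Contraception.** Inclusion criterion 6 in Section 4.1 has women of child-bearing potential "agree to use 2 highly effective methods of contraception throughout study participation and for 75 days after last dose of patisiran in this study". Section 4.4 repeats the period: "throughout study participation, and for 75 days after last dose of patisiran in this study". Men with partners of child-bearing potential have the same length, "for 75 days (ie, a whole spermatogenic cycle) after the last dose of patisiran in this study".
- **Reporting.** Section 9.5.2 covers a female patient found pregnant while taking part, and it extends past treatment as follows: "during the first month after receiving the last dose of patisiran, the Investigator should report the pregnancy to the CRO". The report is due no later than 24 hours from when the investigator is told. The pregnancy is then followed to completion, and certain outcomes go through the SAE route.

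A separate clause in Section 9.5.2 covers pregnancy in a patient's partner. It gives no post-dose time limit.

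Table 1 places the End of Study and Early Withdrawal visits, each with a urine pregnancy test, 4 (+1) weeks after the last dose. Section 4.4 explains why contraception is required: TTR carries vitamin A, lowering TTR lowers vitamin A, and whether this affects reproduction in these patients is not known.

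**The concern.** The protocol asks women to avoid pregnancy for 75 days after the last dose, but requires pregnancies to be reported for only about the first month of that time. A pregnancy first recognised in the remaining weeks need not be reported, and because follow-up to outcome hangs on the same paragraph, its outcome need not be recorded. A contraceptive failure late in the period would then leave no trace in the study data.

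At stake is safety information, not an efficacy conclusion. The protocol states that the reproductive effect of lowered vitamin A is an open question. Each pregnancy in this study is direct evidence on it, and there will probably be few. The Phase 1 summary in Section 1.2 gives context: "TTR levels showed evidence of recovery at Day 28 and return to baseline by Day 70". Required reporting thus ends at roughly the time when recovery was first seen in healthy volunteers.

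**Working it through.** The protocol gives no figure for the mismatch, so there is nothing to reproduce. The check is day arithmetic.

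**Inputs**

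| Quantity | Value | Source |
|---|---|---|
| Contraception period after last dose, C | 75 days | Sections 4.1 (criterion 6) and 4.4 |
| First month after last dose, M | 28, 30 or 31 days (assumption; the protocol does not give it in days) | Section 9.5.2 |
| End of Study or Early Withdrawal visit, with last scheduled pregnancy test, E | Day 28 to Day 35 | Table 1, 4 (+1) weeks |

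**Formula.** A pregnancy is reportable if found on study or in the first month, so required reporting ends at the later of M and E:

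gap = C − max(M, E)

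**Results**

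- Visit at Day 28, month of 28 days: 75 − 28 = 47 days (47/75 = 63%).
- Visit at Day 28, month of 30 days: 75 − 30 = 45 days (45/75 = 60%).
- Visit at Day 28, month of 31 days: 75 − 31 = 44 days (44/75 = 59%).
- Visit at Day 35, any of these months: 75 − 35 = 40 days (40/75 = 53%).

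The gap is therefore 40 to 47 days.

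**Does anything else in the protocol cover those days?**

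- *Adverse event reporting* (Section 9.5) runs from the first dose to the end of the study. For early withdrawals, ongoing events are followed to resolution or 28 days after the last dose.
- *SAE reporting of pregnancy outcomes* (Section 9.5.2) is written for pregnancies the investigator is already following.
- *Scheduled testing* ends with the visit at Day 28 to 35. The Argentina version (3.1) tests monthly, but only during study duration, so it adds nothing afterwards. Its own Section 9.5.2 is not in the text available.

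None of these reaches Day 75.

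**Detection and conception.** The trigger in Section 9.5.2 is when the patient is found to be pregnant. A conception inside the first month that is recognised later also falls outside required reporting. Counted by conception, the gap is larger than 40 to 47 days. The documents give no detection delay, so the excess cannot be sized.

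**The case against.** The strongest reply is that the point is narrow. The main reporting period is the whole of study participation, in a study estimated to last 5 years, and only the tail after the last dose is short. Only women of child-bearing potential are affected. The percentages are shares of calendar days, not of pregnancies or of risk. Sites may also report later pregnancies voluntarily. All of this stands. It limits the importance of the point, but the two periods still do not match.

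A reader might infer more than the documents support:

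- *That the protocol contradicts itself on what happens to a pregnant patient.* Section 4.3 says "The Investigator may withdraw a patient from the study if the patient" becomes pregnant, and Section 9.5.2 says "Treatment with patisiran will be discontinued in any patient who is found to be pregnant during the study". The first concerns leaving the study and the second concerns treatment. Stopping drug can be mandatory while study withdrawal stays discretionary, so the two are compatible.
- *That a pregnancy in the later weeks breaches Section 4.4.* That section requires contraceptive use. A failure in a compliant patient breaches nothing, and a pregnancy found after the first month may have been conceived earlier.
- *That the 75 days are a stated risk period.* Vitamin A is the reason given for contraception. The only reason given for the length is the spermatogenic cycle, which concerns men. The protocol does not link the Day 70 recovery figure to the 75 days.
- *That these weeks produce no pregnancy data at all.* The partner clause has no one-month cut-off, so partner pregnancies are not excluded.
- *That reported pregnancies here are the only human evidence.* Other patisiran studies exist, and nothing shown says what pregnancy data they hold.

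**Conclusion.** The concern holds for female patients. As written, 40 to 47 days of the 75-day contraception period (45 with a 30-day month) carry no required pregnancy reporting and no required follow-up to outcome, and the last scheduled pregnancy test falls by Day 35.

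This rests on two readings: that a month is 28 to 31 days, and that a patient's time on study ends with her End of Study or Early Withdrawal visit. The conclusion is the same across that range. The same two periods stand in versions 1.0 and 2.0, so this is not a by-product of an amendment.

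No efficacy analysis is affected. It is a modest gap in safety data collection that should be closed because closing it is cheap. Which contraception period is right is not judged here.

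**What to change.** Reconcile Section 9.5.2 with Section 4.4 so that the pregnancy-reporting window for female patients is not shorter than the contraception period the protocol sets. Defining its end by reference to Section 4.4, rather than by a separate number, would keep the two from drifting apart. In the same sentence, state the post-dose window for partner pregnancies, which is now open. It would also help to say whether the window applies to the date of conception or the date of detection.

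The change concerns data collection only. It costs about one sentence and an instruction to patients to call the site if they become pregnant after their last visit, with slightly longer passive follow-up. The reporting form, the 24-hour route and the follow-up to outcome already exist. No visit or test is added.

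No change to Section 4.3 is needed for this point.

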## 10. STATISTICS

### 10.1. Sample Size

This is an open-label extension study enrolling patients who have previously completed a patisiran study; the size of the study is not determined via power analysis of particular hypotheses tests.

### 10.2. Statistical Methodology

Statistical analyses will be primarily descriptive in nature.

For categorical variables, summary tabulations of the number and percentage of patients within each category (with a category for missing data) will be presented. For continuous variables, the number of patients, mean, median, standard deviation, minimum, and maximum values will be presented.

All data will be provided in by-patient listings.

#### 10.2.1. Populations to be Analyzed

The following patient populations (ie, analysis sets) may be evaluated and used for presentation of the data:

- Full Analysis Set: All patients who were enrolled will be included in the full analysis set. The full analysis set will be the primary set for the analysis of efficacy data.
- Safety Analysis Set: All patients in the full analysis set who received patisiran. The safety analysis set will be used for the analysis of safety assessments.

